	
*A small number of patients may have completed treatment and continued with Visit F1a and/or Visit F2a post-treatment follow-up assessments before the initial availability/approval of the OLE. In these patients, assessments completed at Visit 8 or Visit F2a (as applicable) may be used to confirm eligibility for the OLE. Similarly, a small number of patients may be nearing completion of the DBP at the time of approval of the amendment which requires a dilated ophthalmic examination, these patients must complete the dilated ophthalmic examination prior to entry in the OLE and as such, may experience a delay of up to a few weeks from Visit 8 prior to entry in the OLE.
 
The study day for all subsequent visits as outlined in Table 1b will be calculated from the date that Visit 8A is conducted.
 
**Note: Patients who successfully completed 52 weeks of OLE treatment with XEN1101 (as per Protocol version 4.1) prior to approval of the amendment in Protocol version 4.2, and in whom it has been <6 months since their last treatment, will be permitted to resume OLE treatment with XEN1101 if they continue to meet criteria for participating in the OLE. This subgroup of patients will need to reconsent and complete Visit 14A assessments onsite in order to obtain study drug and paper diary. A urine pregnancy test must be performed for females of childbearing potential (if positive a serum pregnancy test will be performed).
 
Exclusion Criteria:
 
1. Patients who met any of the withdrawal criteria in the DBP.2. Any medical condition, personal circumstance, or ongoing AE that in the opinion of the investigator exposes the patient to unacceptable risk by participating in the OLE, or prevents adherence to the protocol.3. Females who are pregnant, breastfeeding, or planning to become pregnant until 6 months after the last dose of study drug.4. Patients planning to enter a clinical trial with a different investigational drug or plan to use any experimental device for treatment of epilepsy or any other medical condition.

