Study Week	8	11	23	35	47	60	73	86	99	112	125	138	151	164	165	170	
Informed consent							X ^I										
C-SSRS	-	X	X	X	X	X	X	X	X	X	X	X	X	X	X	X	X
Eligibility assessment	X																
Adverse events	-	X	X	X	X	X	X	X	X	X	X	X	X	X	X	X	X
Physical and neurologic (including non-dilated ophthalmic) examinations	-	X	X	X	X	X		X		X		X		X	X	X	X
Dilated ophthalmic examination ^A						X		X ^A		X ^A		X ^A			X ^A		X
Vital signs ^B	-	X	X	X	X	X		X		X		X		X	X	X	X
Weight, body mass index	-	X	X	X	X	X		X		X		X		X		X	X
Electrocardiogram (12-lead)	-	X	X	X	X	X				X				X	X	X	X
AUA Symptom Index	-	X	X	X	X	X		X		X		X		X		X	X
Concomitant medications	-	X	X	X	X	X	X	X	X	X	X	X	X	X	X	X	X
Pregnancy test ^C	-	X	X	X	X	X	X ^I	X		X		X		X		X	X
Clinical laboratory tests	-	X	X	X	X	X		X		X		X		X	X	X	X
QoL assessments (QOLIE-31)	-		X	X	X			X		X		X		X		X	X
Clinical Global Impression of Severity (CGI-S)	X		X	X	X	X	X	X	X	X	X	X	X		X	X	
Patient Global Impression of Severity (PGI-S)	X		X	X	X	X	X	X	X	X	X	X	X		X	X	
Collect eDiary, Issue/Training of paper diary ^D	X																
Collect and compliance check of completed paper diary and issue new paper diary		X	X	X	X	X	X ^I	X		X		X		X	X	return	return
PK blood samples (XEN1101) ^E	-	X				X				X				X			X
Study drug compliance check	-	X	X	X	X	X		X		X		X		X			X

Study Period	Open-label Treatment														Post-Tx Follow-up ^{F,G}		
Visit Number	8A*	9	10	11	12	13A	14A-TC ^I	15A ^I	16-TC	17	18-TC	19	20-TC	21	F1b	F2b	ET
Study Day	56±3	77±3	161±7	245±7	329±7	420±7	511±7	602±7	693±7	784±7	875±7	966±7	1057±7	1148±7	1155±3	1190±10	
Study Week	8	11	23	35	47	60	73	86	99	112	125	138	151	164	165	170	
Dispense study drug to patient	X	X	X	X	X	X	X ^H	X	X ^H	X	X ^H	X	X ^H				

*: Last day of double-blind treatment period. Patients entering the OLE will be dispensed 20 mg QD of XEN1101 and return their previous study drug.

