2 INTRODUCTION

2.1 STUDY RATIONALE

XEN1101 is a novel, small molecule, selective KCNQ2/3 ($K_v7.2/7.3$) potassium channel positive allosteric modulator being developed for the treatment of partial-onset (focal) epilepsy. Enhancing the open state of KCNQ2/3 in neurons favors a hyperpolarized resting state, which reduces rapid action potential spiking. **CCI**

XEN1101 was investigated at single doses of 5, 15, 20, 25, and 30 mg, as well as multiple doses of 15 or 25 mg once daily (QD) for up to 10 days in healthy volunteers. The influence of single doses was also investigated for effects on cortical and corticospinal excitability using transcranial magnetic stimulation (TMS) techniques. XEN1101 was well tolerated, adverse events (AEs) were generally transient, dose/exposure related, and the majority of AEs were mild. The most common related AEs were central nervous system (CNS) effects such as dizziness and sedation, consistent with this class of drugs (antiepileptics). The pharmacokinetics (PK) of XEN1101 were found to be suitable for QD dosing, with absorption of the drug enhanced by food. The terminal elimination half-life was approximately 1 week after repeat dosing in healthy volunteers. The results from the TMS studies in healthy volunteers suggest that the plasma levels expected at the dose regimens to be used in this study are anticipated to decrease cortical excitability and may suppress seizures in epilepsy patients. For detailed summaries of the results of these studies, please see the Investigator's Brochure.

The purpose of this Phase 2 clinical trial is to evaluate the safety, tolerability, and efficacy of XEN1101 as adjunctive therapy in adults with focal-onset epilepsy. For this study, plasma levels expected at the doses chosen were shown to be well tolerated in the first-in-human (FIH) study (XPF-008-101a) and pharmacologically active in the brain in the companion TMS crossover study (XPF-008-101b).

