6.3 MEASURES TO MINIMIZE BIAS: RANDOMIZATION AND BLINDING

During the DBP, IMP will be administered under double-blind conditions: Patients and investigators will be blinded to treatment assignment. Sponsor and CRO staff will also remain blinded with the exception of a pre-identified individual from the sponsor. If there is a medical need to reveal the assigned dose administered to a patient, the code break procedures as described by the IRT provider will be followed. In the event of an emergency, it is the investigator’s responsibility to evaluate the necessity of unblinding the patient’s treatment assignment. If the investigator proceeds with the unblinding, he/she should notify the medical monitor as soon as feasible that the unmasking event occurred, without revealing the result of the unblinding.

Training will be provided to site staff regarding ways to minimize the placebo response effect.

Randomization will be stratified by background use versus non-use of a CYP3A4 inducer medication (eg, any of carbamazepine, eslicarbazepine, oxcarbazepine, phenytoin, topiramate, or phenobarbital).

During the OLE, all participants will receive 20 mg XEN1101 capsules. The participants and investigators, as well as sponsor and CRO staff, will remain blinded to prior treatment assignments until all patients have completed the DBP and the database has been locked for that phase of the study.

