- Physical and neurologic examinations, including ophthalmoscopy.
- Vital signs.
- 12-lead ECG.
- Concomitant medications, including any changes to AEDs.
- Site check of eDiary compliance.
- Clinical laboratory tests.
- Blood sample for PK analysis (XEN1101).
- CCI

Visit F2a – Study Day 98 (42 ± 7 days post last dose) in patients NOT entering the OLE

Upon completion of Visit F2a (or the ET visit, when applicable), the patient's participation in the study will be finished. The following assessments should be completed at Visit F2a:

- C-SSRS.
- AEs.
- Physical and neurologic examinations, including ophthalmoscopy.
- Vital signs.
- Weight and BMI.
- 12-lead ECG.
- AUA Symptom Index.
- QoL assessment (QOLIE-31).
- CGI.
- PGI-C.
- Concomitant medications, including any changes to AEDs.
- Site check of eDiary compliance.
- Urine pregnancy test for females of childbearing potential (if positive a serum pregnancy test will be performed).

- Clinical laboratory tests.
- Blood sample for PK analysis (XEN1101).
- Return of eDiary device.

Unscheduled Visit(s)

Patients may return to the site between scheduled study visits as required for safety management, eDiary re-training/maintenance or for other reasons. The investigator will determine the tests and procedures to be performed at an unscheduled visit, which should be recorded in the source and eCRF.

Early Termination (when applicable)

If the patient discontinues or is withdrawn from the study, and is unwilling or unable to complete the follow up visits (F1a and F2a), efforts should be made to complete the ET evaluations and report the observations up to the time of withdrawal as thoroughly as possible. The following assessments should be performed on the last day the patient was treated with the IMP or as soon as possible thereafter:

- C-SSRS.
- AEs.
- Physical and neurologic examinations, including ophthalmoscopy.
- Vital signs.
- Weight and BMI.
- 12-lead ECG.
- AUA Symptom Index.
- QoL assessment (QOLIE-31).
- CGI.
- PGI-C.
- Concomitant medications, including any changes to AEDs.
- Site check of eDiary and IMP compliance.
- Urine pregnancy test for females of childbearing potential (if positive a serum pregnancy test will be performed).
- Clinical laboratory tests.
- Blood collection for biomarker assessment (not mandatory for inclusion in the study).
- Blood sample for PK analysis (XEN1101).
- Collect remaining IMP supply from patient.
- Return of eDiary device.
- CCI

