PROCEDURES FOR PATIENTS ENTERING THE OLE

Upon successful completion of all study visits in the DBP up to and including Visit 8 (Study Day 56), patients may be considered for entry into the OLE. Eligible patients continuing in the OLE will stop their double-blinded dosing as per protocol, complete the Day 56/Visit 8 procedures (including the additional procedures outlined below and in [Table 1b](#)), and return the eDiary device. Participants will begin dosing with XEN1101 at a 20 mg QD dose (at least 1 day following their last blinded dose) for the duration of the OLE. Subsequent visits will be conducted as outlined in the Schedule of Assessments, [Table 1b](#), and as described below.

Visit 8/Study Day 56 (\pm 3 days) End of DBP and Start of OLE

For patients entering the OLE, the following assessments should have been performed at the end of the 8-week DBP and after administration of the last blinded dose (and do not need to be duplicated):

- C-SSRS.
- AEs.
- Physical and neurologic examinations, including ophthalmoscopy.†
- Vital signs.
- Weight and BMI.
- 12-lead ECG.
- AUA Symptom Index.
- QoL assessment (QOLIE-31).
- Clinical Global Impression (CGI) of change.
- Patient Global Impression of Change (PGI-C).
- Concomitant medications, including any changes to AEDs.
- Site check of eDiary and IMP compliance.
- Urine pregnancy test for females of childbearing potential (if positive a serum pregnancy test will be performed).
- Clinical laboratory tests.
- Blood collection for biomarker assessment (not mandatory for inclusion in the study).
- Blood sample for PK analysis (XEN1101).
- Collect remaining IMP supply from patient.

CCI

ADDITIONAL VISIT 8A PROCEDURES FOR PATIENTS ENTERING THE OLE

For patients entering the OLE, the following assessments should also be performed:

- Eligibility assessment for OLE.
- Return of eDiary.
- Training and supply of paper diary.
- Clinical Global Impression of Severity (CGI-S).
- Patient Global Impression of Severity (PGI-S).
- Dispense study drug for OLE (20 mg capsules XEN1101).

Visit 9/Study Day 77 (\pm 3 days) – Patients Participating in the OLE

- C-SSRS.
- AEs.
- Physical and neurologic examinations, including ophthalmoscopy.
- Vital signs.
- Weight and BMI.
- 12-lead ECG.
- AUA Symptom Index.
- Concomitant medications, including any changes to AEDs.
- Urine pregnancy test for females of childbearing potential (if positive a serum pregnancy test will be performed).
- Clinical laboratory tests.

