- QoL assessment (QOLIE-31).
- Blood sample for PK analysis (XEN1101).
- Collect and check completed diary and resupply of new paper diary.
- Compliance check and return of study drug (20 mg capsules XEN1101).
- CCI

Note: Patients who successfully completed 52 weeks of OLE treatment (as per Protocol version 4.1) prior to approval of the amendment in Protocol version 4.2, and in whom it has been <6 months since their last treatment, will be permitted to resume OLE treatment with XEN1101 if they continue to meet study criteria for participating in the OLE. This subgroup of patients will need to reconsent and complete Visit 14A assessments onsite in order to obtain study drug and the paper diary. A urine pregnancy test must be performed for females of childbearing potential (if positive a serum pregnancy test will be performed).

TC Visit 14A/Study Day 511 (± 7 days) – Patients Participating in the OLE

- Reconsent (for patients reentering the OLE)
- C-SSRS.
- AEs.
- Concomitant medications, including any changes to AEDs.
- Urine pregnancy test for females of childbearing potential (if positive a serum pregnancy test will be performed) (for patients reentering the OLE).
- CGI-S.
- PGI-S.
- Provision of study drug (20 mg capsules XEN1101) to patient.

Visit 15A/Study Day 602 (± 7 days) – Patients Participating in the OLE

- C-SSRS.
- AEs.
- Physical and neurologic examinations, including ophthalmoscopy.
- Vital signs.
- Weight and BMI.
- AUA Symptom Index.
- Concomitant medications, including any changes to AEDs.
- Urine pregnancy test for females of childbearing potential (if positive a serum pregnancy test will be performed).
- Clinical laboratory tests.
- CGI-S.
- PGI-S.
- QoL assessment (QOLIE-31).
- Collect and check completed diary and resupply of new paper diary.
- Compliance check and return of study drug (20 mg capsules XEN1101).

- CCI

TC Visit 16/Study Day 693 (\pm 7 days) – Patients Participating in the OLE

- C-SSRS.
- AEs.
- Concomitant medications, including any changes to AEDs.
- CGI-S.
- PGI-S.
- Provision of study drug (20 mg capsules XEN1101) to patient.

Visit 17/Study Day 784 (\pm 7 days) – Patients Participating in the OLE

- C-SSRS.
- AEs.
- Physical and neurologic examinations, including ophthalmoscopy.
- Vital signs.
- Weight and BMI.
- 12-lead ECG.
- AUA Symptom Index.
- Concomitant medications, including any changes to AEDs.

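### Patients already past Visit F2a may start open-label 20 mg on F2a results of any age, with no pregnancy test or C-SSRS scheduled until Visit 9

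*Combined protocol and SAP*

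**What the plan says.** - **Late first entry.** The single-asterisk note to the OLE entry criteria (Synopsis, repeated in Sections 4.2 and 5.3) covers a small number of patients who went on to Visit F1a and/or F2a before the OLE first became available. It says: "In these patients, assessments completed at Visit 8 or Visit F2a (as applicable) may be used to confirm eligibility for the OLE". None of the three places limits the age of those results. The note also restarts the OLE day count at the actual date of Visit 8A, so it expects some Visits 8A to fall well after Visit 8.
- **Table 1b, Visit 8A column.** The C-SSRS and pregnancy-test rows show a dash, and their first mark is at Visit 9. The eligibility assessment and dispensing are marked at Visit 8A. The column's footnote reads: "Last day of double-blind treatment period. Patients entering the OLE will be dispensed 20 mg QD of XEN1101 and return their previous study drug".
- **Section 8.1, patients entering the OLE.** The Visit 8 assessments are taken as done "after administration of the last blinded dose (and do not need to be duplicated"). The extra list for Visit 8A holds the OLE eligibility assessment, the exchange of diaries, CGI-S, PGI-S and dispensing.
- **Restart at Visit 14A.** Patients who had completed 52 weeks of OLE under version 4.1, "and in whom it has been <6 months since their last treatment", may resume. They must reconsent and attend Visit 14A on site, where Section 8.1 lists: "Urine pregnancy test for females of childbearing potential (if positive a serum pregnancy test will be performed) (for patients reentering the OLE").

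**The concern.** The dashes at Visit 8A are sensible when Visits 8 and 8A share a date, because the Visit 8 pregnancy test and C-SSRS are then current. The single-asterisk note allows a later Visit 8A, and nothing says that the dashes stop applying in that case. Read together, the two rules let a site clear a patient on an F2a pregnancy test and C-SSRS of any age and hand over 20 mg capsules the same day.

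What is at stake is patient safety, not inference. Pregnancy is an OLE exclusion, but a pregnancy that the patient does not know of can be found only by a test. Recent suicidal plan or intent is among the entry criteria that must still be met, but no instrument is scheduled to look for it. For someone past F2a, Visit 8A is in effect a new start of drug. For those who had placebo it is the first exposure, and they cannot be picked out, because participants and staff "will remain blinded to prior treatment assignments until all patients have completed the DBP and the database has been locked".

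**Working it through.** No power, alpha or sample-size figure bears on this point. The check compares the protocol's rules and counts days.

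**1. The protocol's dosing starts side by side** (Tables 1a and 1b, Section 8.1)

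| Start of dosing | Limit on the gap | Pregnancy test before drug | C-SSRS before drug |
|---|---|---|---|
| Day 0 (Visit 3) | not applicable | scheduled | scheduled |
| Visit 8A on the Visit 8 date | none needed | scheduled, as part of Visit 8 | scheduled, as part of Visit 8 |
| Visit 8A after F2a | none stated | not scheduled; F2a result may be used | not scheduled; F2a result may be used |
| Visit 14A restart | under 6 months since last treatment | scheduled, added for restarters | scheduled, routine at 14A for all OLE patients |

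Only the third row has neither check tied to the start of drug.

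**2. Time to the next scheduled test.** Visit 9 is Day 77 ± 3 and Visit 8A is Day 56, with days counted from Visit 8A for late entrants: 77 − 56 = 21, so 18 to 24 days after dispensing.

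**3. Whether Visit 8A is a new start.** F2a is 42 ± 7 days after the last blinded dose, so 35 to 49 days. Section 2.1 states: "The terminal elimination half-life was approximately 1 week after repeat dosing in healthy volunteers". At 7 days each, that is 35/7 = 5 to 49/7 = 7 half-lives. Drug remaining is 0.5^5 = 3.1% to 0.5^7 = 0.8%. The randomized share on placebo is 2/(2+1+1+2) = 1/3; the share among late entrants is not given.

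**4. Age of the results.** Let g be the days from F2a to Visit 8A. The F2a results are g days old at dispensing, and the next test comes g + 18 to g + 24 days after F2a. The documents give no g.
- Assumed g = 30: 48 to 54 days.
- Assumed g = 90: 108 to 114 days.
- If the restart limit were borrowed (about 182 days since last dose): g could reach 182 − 49 = 133 to 182 − 35 = 147, and the next test 133 + 18 = 151 to 147 + 24 = 171 days. That limit is written for another group, so this only illustrates scale.

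**5. Exposure of a pregnancy missed at Visit 8A.** Assume dosing starts on the Visit 8A date, stops on the day of the Visit 9 test, and washout takes 5 × 7 = 35 days. Then 18 + 35 = 53 to 24 + 35 = 59 days.

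**6. Neighbouring groups are bounded.**
- Patients who had reached only F1a: F2a falls by day 49, so the Visit 8 pregnancy test is at most 49 days old. F1a is 4 to 10 days after the last dose, so its C-SSRS is at most 49 − 4 = 45 days old.
- Patients delayed by the dilated eye examination: the delay is described as up to a few weeks, and beyond 1 week an F1a visit, which includes a C-SSRS, comes first. With an assumed delay of 1 to 4 weeks, the Visit 8 pregnancy test is 7 to 28 days old, no longer than the DBP's own interval from Visit 6 to Visit 8 (56 − 28 = 28 days).

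**The case against.** The strongest reply is that the group is closed and historical. Only patients who finished before the OLE opened qualify, and the same text speaks of patients who had already completed 52 weeks of OLE under version 4.1. Most late entrants have therefore probably entered. This stands and lowers the priority, although the documents do not confirm it and the permission is still in the text.

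Other points also limit what can be claimed:
- **AEs and medications.** A reader might infer from the dashes that AE and concomitant-medication status also go unchecked. The documents do not support that. The eligibility assessment at Visit 8A must apply an exclusion for ongoing AEs. Section 8.4.4 requires AEs found or reported at any visit to be recorded. The 42-day AE window in Section 8.4.4.1 runs from the last dose, which for these patients is an OLE dose. Section 6.5 has concomitant treatment recorded throughout the study.
- **The restart comparison.** A reader might infer that restarters get a full set of special checks. C-SSRS, AE and medication review are routine at Visit 14A for every OLE patient. Table 1b footnote I adds reconsent, on-site conduct and the urine test, so the contrast holds only for the pregnancy test. The next scheduled test also comes later after 14A (602 − 511 = 91 days, against 21 after 8A).
- **Leaving the study.** Section 8.1 says of F2a that the patient's "participation in the study will be finished". That stands under a heading for patients not entering the OLE, so it does not show that late entrants had left the study.
- **Permissive wording and contraception.** Sites may repeat tests. Section 5.4 requires contraception until 6 months after the last dose, and Section 5.4.3 asks patients to report pregnancy. These lower the risk. Yet restarters are inside the same 6 months and the protocol still tests them, and an unrecognised pregnancy cannot be reported.

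**Conclusion.** The concern holds in narrow form. First-time OLE entrants already past F2a can be cleared on F2a results with no maximum age, and neither a pregnancy test nor a C-SSRS is scheduled before 20 mg once daily is dispensed. The next ones come 18 to 24 days later. The pregnancy test is the firmer half. The C-SSRS half is weaker, because suicidal plan or intent must still be considered at the eligibility assessment.

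The size depends on the unknown gap g, on a half-life of 1 week, and on dosing from the Visit 8A date. A redacted line follows the Visit 8 list in Section 8.1 and cannot be checked, but the relevant rows of Table 1b are not redacted. A reader might infer a general gap covering every delayed entrant. The F1a-only and eye-examination groups are bounded and do not support that. The DBP analysis is unaffected. This is a low-priority safety improvement.

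**What to change.** In the single-asterisk note (Synopsis, Sections 4.2 and 5.3) and in a Table 1b footnote, state that the Visit 8A dashes, and the Section 8.1 allowance not to repeat Visit 8 assessments, apply only when Visit 8A is held on the Visit 8 date. For patients cleared on earlier F2a results, require at Visit 8A, before dispensing, a C-SSRS and, for females of childbearing potential, a urine pregnancy test with a serum test if positive.

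The cost is one footnote, a sentence in each note, and one urine test and one short instrument at a visit already planned, for a small number of patients. The drawback is that the change does little if these patients have already entered the OLE.
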